Our study will implement the caregiver survey and the medical record abstraction tools in the PFK ABD population. Caregivers of all 8,080 newly enrolled ABD children will be invited to participate in the survey. We estimate that our methods will yield 2,750 caregiver survey respondents. The estimated 34% response rate considers a combination of those who are unreachable based on available contact information and those who are reached but who opt out of participation. This sample size will allow us to estimate performance on each survey-based care coordination indicator within a 95% confidence interval of ± 1.5 percentage points (conservatively assuming underlying performance of 50%). Confidence interval widths for age, gender, and urban/rural subpopulations will range from ± 1.8 to ± 3.7 . This sample size will allow us to identify a significant urban/rural difference ($\alpha=0.05$) of 0.05 percentage points (i.e., 0.50 vs. 0.55) with a power of 0.83.

Medical Record Abstraction

Participants & Sample Size

We further estimate that 1,000 of those who complete the survey will consent to a review of their medical records that will allow data collection on medical record review based measures that can be linked to survey data and ultimately medical claims data. This consent rate is based on experience in current pilot work. This sample size will allow us to estimate performance on each medical record-based care coordination indicator within a 95% confidence interval of ± 2.9 percentage points (conservatively assuming underlying performance of 50%). Confidence interval widths for age, gender, and urban/rural subpopulations will range from ± 3.6 to 7.0. This sample size will allow us to identify a significant urban/rural difference ($\alpha=0.05$) of 0.10 percentage points (i.e., 0.50 vs. 0.60) with a power of 0.89.

Analysis

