We will first calculate performance on each of the 31 care coordination measures using data from the FECC and the care coordination medical record review. We will stratify indicator performance by age group, urban/rural residence, and disabling diagnosis (physical vs. mental diagnosis). Where appropriate, performance in our sample will be compared with pilot data collected by COE4CCN. We will then link data from the FECC, the medical record review, and the PFK claims data, at the individual level, to assess the relationship between receipt of care coordination elements and selected outcomes. For example, this linked database will allow us to test the relationship between receipt of a useful and understandable discharge summary following an inpatient stay and 30 day readmission or the relationship between regular communication with a designated care coordinator and use of the emergency department. Specific quality/outcomes measures to be studied will be drawn from claims and EMR-based CHIPRA and HEDIS measures with input from our advisory panel. We expect limited missing data in the survey and medical record data due to our data collection methods. Missing data from the survey and the medical record review will be handled using the “available case

analysis approach” in which all cases with complete data for a selected analysis are included in that analysis.

The proposed analysis in Aim 2 will allow us to 1) quantitatively assess the quality and completeness of care coordination offered to ABD children upon roll-in to the ACO; 2) determine whether that quality and completeness is consistent across selected subpopulations; and 3) understand the relationships between elements of care coordination and patient-centered measures of quality and outcomes.

Aim 3

In Aim 3, we will compare quality, utilization, and other patient-centered outcomes for ABD children before and after joining an ACO in Ohio using claims, survey and medical record data. Our comparative analysis includes both quantitative and qualitative measures identified through Aims 1 and 2. In addition, we will triangulate findings from our quantitative, qualitative and care coordination assessment analyses to provide a robust and multi-faceted analysis of the comparative effectiveness of care coordination under a fee-for-service system compared to an ACO model for children with disabilities.

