We expect 35% percent of those completing the telephone survey to consent to medical record abstraction.

- *Prevention of missingness* – The script requesting medical record access will clearly explain the reason for access and the processes for maintaining confidentiality.
- *Monitoring of missingness*– We will describe the lost respondents by gender, age, urban/rural residence, and diagnosis category using claims data. We will also test the relationship between perceptions of care coordination and consent to medical record abstraction using data from the telephone survey.

A consort-style diagram will be used to illustrate potential participant loss or refusal at each stage of the study **(MD-4)**.

Aim 3 – Utilization Analysis

Over 95% of the population will be included in claims data analysis looking at overall pre-/post-policy change utilization analysis. The primary risk of missingness for this analysis is failure of successful linking between the FFS (pre) and PFK (post) data. After acquisition of the data, we will first assess the data quality. Like the traditional Medicaid plan, PFK reimburses physicians

on the basis of services provided (fee-for-service), therefore we expect that the payment data and other fields such as patient id, date of service, and procedure codes required for reimbursement will be populated for each claim billed to Medicaid/PFK. The demographic files (e.g. gender, race) may also have missing data, which is anticipated to be proportionally small, based on the team's prior experience with claims.

- Prevention of missingness – We will investigate each non-match. When there is no matching Medicaid ID across the two databases, we will directly check the record to identify potential transposition or typographical errors. If no such error can be found, we will attempt to use probability matching using date of birth, zip code of residence, gender, and soundex last name to link records.
- Monitoring of missingness– We will calculate and report the final “no-match” rate between PFK and state FFS data.

Statistical methods and sensitivity analysis to handle missing data (MD2, MD3, MD5)

Aim 2 – Caregiver Survey

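### The test of chart-review consent against perceived care coordination feeds no analysis, so the stated ±2.9 points leaves out a consent bias that would exceed it if consenters and non-consenters differ by more than about 4.5 points

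*Combined protocol and SAP*

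**What the plan says.** The sample-size text for Medical Record Abstraction (Aim 2) expects that "1,000 of those who complete the survey will consent to a review of their medical records". It gives a 95% interval of ±2.9 points for each record-based indicator at an underlying performance of 50%. The survey is expected to yield 2,750 completers from 8,080 invited caregivers.

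The section Handling Missing Data (MD-1) puts the consent share as follows: "We expect 35% percent of those completing the telephone survey to consent to medical record abstraction". Under monitoring of missingness it will describe non-consenters by gender, age, urban/rural residence and diagnosis category, and then adds: "We will also test the relationship between perceptions of care coordination and consent to medical record abstraction using data from the telephone survey". A flow diagram will show losses at each stage.

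The Aim 2 Analysis section handles missing survey and record data by available-case analysis, "in which all cases with complete data for a selected analysis are included in that analysis". The later section on statistical methods and sensitivity analysis (MD2, MD3, MD5), under its Aim 2 caregiver-survey heading, rules out imputation. It plans a sensitivity analysis for differential non-response on the same four variables and states that differential missingness is not hypothesised.

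**The concern.** About 65% of survey completers are expected to drop out at the consent step. Perceived coordination is the variable the plan singles out as possibly related to consent, and it could plausibly also be related to what the chart shows. It is recorded for refusers too, because consent is requested at the end of the interview. Yet its only use at this step is a stand-alone test.

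If families with better-coordinated care consent more often, record-based indicators that track perception would be too high, and Aim 2 exists to judge how good and complete the ACO's coordination is. The chart data also feed the linked survey-chart-claims analyses. A p-value neither measures nor removes the resulting error. The plan is more careful with a much smaller loss: for Aim 3 it expects over 95% inclusion and still pre-specifies bounds at the 10th and 90th percentiles for unlinked cases.

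**Working it through.** **1. The plan's own precision figure.** Half-width = 1.96 × √(p(1−p)/n) × √((N−n)/(N−1)).

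- n = 1,000, p = 0.50, no finite population correction: 3.10 points.
- N = 8,080: 3.10 × √(7,080/8,079) = 2.90, which reproduces the stated ±2.9.
- N = 2,750: 2.47, which does not.
- The same formula with n = 2,750 and N = 8,080 gives 1.52, matching the survey's stated ±1.5.

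So ±2.9 treats the charts as a simple random sample of all 8,080 children. It holds no allowance for selection. (35% of 2,750 is 962.5 rather than 1,000, and 1,000/2,750 is 36.4%. With 963 charts the half-width is 2.96.)

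**2. Consent bias relative to all survey completers.** With consent rate r, and chart performance P1 in consenters and P0 in non-consenters:

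bias = P1 − [r·P1 + (1−r)·P0] = (1−r)(P1−P0) = 0.65 × gap at r = 0.35.

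Threshold: 2.9/0.65 = 4.46 points (4.56 at r = 36.4%). The gap is not in the documents, so a range is shown:

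| Assumed gap (points) | Bias (points) |
|---|---|
| 2 | 1.3 |
| 4 | 2.6 |
| 5 | 3.25 |
| 10 | 6.5 |
| 15 | 9.75 |

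Taking the standard error as 2.9/1.96, the nominal 95% interval covers the survey-completer value about 49% of the time at a 4.5-point gap, 41% at 5 points and under 1% at 10 points.

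**3. Two-group illustration.** Assumptions: half of completers report a coordinator, overall consent is 35%, and mean chart performance is 45%.

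Bias = (0.5·c1·p1 + 0.5·c0·p0)/0.35 − 0.45, where c is consent and p is chart performance with (1) and without (0) a coordinator.

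Design effect of consent weights = 0.35 × 0.5 × (1/c1 + 1/c0).

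| Consent c1 vs c0 | Bias, p 60% vs 30% | Bias, p 55% vs 35% | Bias, p 50% vs 40% | Design effect | 2.90 × √(design effect) |
|---|---|---|---|---|---|
| 40% vs 30% | 2.1 | 1.4 | 0.7 | 1.021 | 2.93 |
| 45% vs 25% | 4.3 | 2.86 | 1.4 | 1.089 | 3.03 |
| 50% vs 20% | 6.4 | 4.3 | 2.1 | 1.225 | 3.21 |

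Three of the six cells in the first two bias columns exceed 2.9, and none in the third does.

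**4. Why the test cannot stand in for an adjustment.** With 40% vs 30% consent, coordinator reports run at 0.40/0.70 = 57.1% among consenters and 0.60/1.30 = 46.2% among non-consenters, an imbalance of about 11 points. With 1,000 against 1,750 people, power to detect even a 10-point imbalance around 50% is 99.9%. The test would almost surely be significant, yet the bias in that row is 0.7 to 2.1 points. In the other direction, a 4.5-point imbalance is detected with power of only 62%. Significance therefore says little about whether ±2.9 is exceeded.

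**The case against.** The plan is not silent on consent loss. It describes non-consenters, draws a flow diagram and runs the test as a diagnostic. The consent paragraph may fall under the same caregiver-survey heading as the sensitivity analysis and names the same four variables, so that analysis may reach the consent step. This stands, but under either reading perceived coordination is left out.

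A reader might infer that the sponsor suspects consent depends on perception. The documents do not support that: differential missingness is expressly not hypothesised.

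The size rests wholly on assumed gaps. This also stands, and is why the point is conditional.

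A simple weight model on CC2 and CC10 could not be fitted to all respondents. Under Attachment B, CC2 is scored only if Q2=1, and CC10 only if Q2=1 and Q3=1, where Q3 is the CC2 item itself. Wherever CC10 exists, CC2 is therefore constant. Don't-know, refused and blank answers also occur. This is correct, and the fix allows for it.

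The consent request also covers linking survey answers to records and claims, so joining refusers' answers to other data might be questioned. This does not block the fix. The plan already stratifies survey indicators by age, residence and diagnosis, already describes non-consenters on the four variables, and the weights could use survey answers alone.

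Finally, the main before/after comparison uses claims and does not depend on chart consent. That is so, and it limits the point to Aim 2 and the linked analyses.

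**Conclusion.** The gap in the plan is real: no analysis adjusts or qualifies the record-based indicators for consent related to perceived coordination, although the plan tests for exactly that. The consequence is conditional. Bias relative to survey completers exceeds the stated ±2.9 only if consenters and non-consenters differ by more than about 4.5 points in chart performance, and its sign follows the sign of that difference.

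Two stronger readings go beyond the documents. One is that every chart indicator is inflated by more than its margin. That would need a known gap and would need each documentation measure to track caregiver perception, and neither is shown. The other is that the linked analyses describe only satisfied families. In the illustration, 0.25/0.70 = 36% of the chart sample has no coordinator at 45% vs 25% consent, and 0.20/0.70 = 29% at 50% vs 20%. Linked models that already condition on the survey score driving consent are also less affected. Bias in those associations has not been quantified.

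This is a correctable gap in pre-specification that should be closed. It does not undermine the study's main comparison.

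**What to change.** Pre-specify, beside the unweighted record-based indicators, estimates weighted by the inverse probability of consent. Model consent among all survey completers on:

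- a three-level coordination item defined for everyone: one provider or service only (Q2 not 1), no coordinator, has a coordinator, with a further category for missing answers;
- CC10 only as a term nested within those who have a coordinator;
- indicators with no screener item, such as SCP2 and SCP6;
- age, gender, urban/rural residence and diagnosis category.

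Use the same weights in the linked chart analyses as a sensitivity analysis. Report the size of the consent-by-perception association, not only its p-value. State that ±2.9 covers sampling error alone.

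The change is to the analysis only and needs no new data collection. Precision falls modestly: in the illustrations ±2.9 becomes at most about ±3.2, and a model with more covariates may cost more. The weights remove only selection explained by measured answers, so a simple bound over a range of residual consenter/non-consenter gaps should accompany them. They also restore representativeness only to the 2,750 survey completers. The 1,000 charts are 12.4% of the 8,080 children, and survey non-response remains a separate step.

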Administrative data-derived measures include items such as continuity of care, use of the emergency department, hospitalizations, and access to primary and specialty care, timely follow-up after initial prescriptions of ADHD medications or after psychiatric hospitalization.[45,46] We will incorporate recent methodological advances in operationalizing these measures from administrative data.[47] All study measures will be reviewed with our Patient Advisory Panel in order to prioritize the measures determined to be of greatest importance to our patient population. The Patient Advisory Panel may also propose and prioritize additional patient-centered outcome measures during the first two years of the project.

Key treatment variable: The key variable of interest is the enrollment in the ACO by children with disabilities. This “treatment” was assigned to children seen by one of the health care facilities within PFK’s 34-county service area in Ohio beginning in July 2013. Data from PFK-enrolled children prior to enrollment (July 2010 – June 2013) will serve as primary controls, adjusting for age and length of time on Medicaid. Children who were enrolled in Ohio Medicaid with ABD eligibility in other areas of the state will serve as additional potential controls using Medicaid claims data. We cannot use these children as primary controls due to important limitations in the data, namely the inability to attribute children to other ACOs outside the 34 county PFK region. PFK’s unique arrangement with the state allows us to clearly identify the ACO catchment area by county and thus we can clearly attribute these patients to PFK.

Patient Characteristics: Our analysis is conducted on a diverse population of children and adolescents. Their characteristics vary by age, gender, race, Latino ethnicity, SSI status, county of residence, diagnoses, procedures received, length of time on Medicaid and other patient characteristics as detailed in **Appendix F**. We will create baseline disease adjustment categories using the Chronic Illness and Disability Payment System, which was specifically designed for disabled Medicaid enrollees. [48]

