The underlying population for this study is all children up to age 18 enrolled in the Partners for Kids (PFK) on May 30th 2015 who had been previously enrolled in fee-for-service (FFS) Medicaid and transitioned into PFK as a result of the ABD policy change. The primary analytic data comes from Ohio Medicaid administrative claims. Claims data have different missing data issues than do other primary or even secondary data sets on several dimensions. First, many of the fields are mandatory, which means fields such as procedure code and Medicaid eligibility status will

be 100% complete. Second, although claims data have the traditional limitations of any administrative data, including the lack of information of services paid fully out-of-pocket or financed through Medicare, only services provided through Medicaid will be used in the analysis, which will take a Medicaid/agency perspective. This means that services and expenditures will not aim to be a complete record, but those covered through the Medicaid program. We will clearly indicate the scope of analysis in publications. For the subsets of claims data merged with survey and medical records, we do not anticipate missing data problems for the same reasons above.

The estimated size of this population is 8,000. Because of the qualitative nature of Aim 1 we do not propose a missing data plan. The following assumptions have been made regarding rates of participation from this population for Aims 2 and 3:

Aim 2 – Caregiver Survey

We expect 34% percent of the eligible caregivers to complete the caregiver survey. This is based on assumptions from previous studies with this population regarding degree of incorrect addresses for the opt-out mailing, opt outs, missing/non-functional telephone numbers, and refusal when contacted.

- *Prevention of missingness*– We will use alternative sources of contact information (e.g. EHR records, internet look-up sites) for those families with missing telephone numbers.
- *Monitoring of missingness* – we will record and report the following statistics: % of invitation letters returned by the post office, % opting out, % bad telephone numbers that cannot be found after research, and % refusal by reached families. For each of these percentages, we will describe the lost respondents by gender, age, urban/rural residence, and diagnosis category using PFK data (note: race is not reliably available on the PFK data).

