Methods for statistical handling of missing responses on the Family Experiences of Care Coordination survey are documented in the survey's scoring guide. We will use these methods to assure that our results are consistent with those being generated in other implementations of the survey. Missing data will not be imputed, however, we will use sensitivity analysis to estimate the effect of differential non-response by age, gender, urban/rural residence, and diagnosis category. We do not hypothesize differential missingness.

Aim 3 - Utilization Analysis

The pre-/post-policy change utilization analysis will be performed on all individuals where we are able to link FFS and PFK claims. We expect a low non-link rate. However, to estimate the impact of the missing data, we will conduct sensitivity analysis by testing change in setting-specific utilization if all the unlinked cases were at the 90th percentile of their age/gender/diagnosis category group and if all unlinked cases were at the 10th percentile of their age/gender/diagnosis category group.

For time invariant missing variables in the FFS or PFK data, such as gender or race, we will carry the last observation forward, assuming gender and race is unchanged for each individual. In the rare case of substantial amount of other types of missing data in the claims, we will employ Multiple Imputation (MI) methods to generate imputations for the missing values, from predicted probabilities estimated based on the complete data (observed and missing data).

Procedures

Aim 1

In all aspects of Aim 1, we will use purposive sampling, attempting to get a mix of participants and to maximize the diversity of our sample in terms of perspectives that we expect to be

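### Aim 2 survey indicators at 34% expected response: no non-response weight is named, and the planned check of unstated method omits prior health-care use and disease burden

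*Combined protocol and SAP*

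**What the plan says.** - Aim 2, Caregiver Survey, Participants & Sample Size: "Caregivers of all 8,080 newly enrolled ABD children will be invited to participate in the survey". Of these, 2,750 (34%) are expected to respond. On the losses: "The estimated 34% response rate considers a combination of those who are unreachable based on available contact information", together with those who are reached and decline. The section states a 95% interval of ±1.5 points for each survey indicator at an assumed performance of 50%.
- Aim 2, Analysis: missing survey data are handled by available-case analysis. No weight is named there or elsewhere.
- Section on handling missing data, prevention and monitoring (MD-1), caregiver survey: returned letters, opt-outs, bad telephone numbers and refusals are to be counted, and each group of lost respondents described by gender, age, urban/rural residence and diagnosis category.
- Statistical methods and sensitivity analysis to handle missing data, Aim 2: missing answers follow the survey's scoring guide, for consistency with other users of the instrument. There is no imputation, but "we will use sensitivity analysis to estimate the effect of differential non-response by age, gender, urban/rural residence, and diagnosis category". The next sentence reads "We do not hypothesize differential missingness". No method is given for the sensitivity analysis.
- Aim 3, Data & Sample Size: claims with utilization, diagnoses and expenditure are available for the same 8,080 children. Under Patient Characteristics: "We will create baseline disease adjustment categories using the Chronic Illness and Disability Payment System" (CDPS below).

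**The concern.** Two thirds of the invited caregivers are expected not to answer. Available-case analysis and the scoring guide deal with blank items in a returned survey; neither deals with a caregiver who never took part. For that, the plan relies on the sensitivity analysis and its four variables.

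The documents themselves suggest that response may track contact with the health system. Missing or dead telephone numbers are repaired partly from electronic medical records (MD-1; Caregiver Survey Methodology), and Medical Record Review estimates that only 50% of the enrolled children were seen in the hospital system in the past year. Families in recent contact may be easier to trace and may also report more coordination. None of the four variables measures amount of use or severity; the only diagnosis split that Aim 2 defines is physical versus mental.

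Two results are exposed. One is the level of each indicator, since Aim 2 sets out to describe coordination for the whole group moved into the ACO. The other is the association between coordination and outcomes such as emergency department use, because prior use could drive both selection into the survey and the outcome.

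The plan is also uneven. For the expected under 5% of children whose claims cannot be linked, it specifies bounds at the 10th and 90th percentiles. For 66% survey non-response it specifies no method.

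**Working it through.** **Inputs from the plan.** N = 8,080 invited; n = 2,750 respondents; p = 50%; stated half-width ±1.5 points.

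**1. Response rate.** 2,750 / 8,080 = 34.0%, so non-response is 66.0%.

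**2. The plan's precision figure.**
- Without finite population correction: 1.96 × √(0.25 / 2,750) = 1.87 points.
- With correction √((8,080 − 2,750) / 8,079) = 0.812: 1.87 × 0.812 = 1.52 points.

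The stated ±1.5 reproduces only with the correction, which treats the respondents as a random sample of the 8,080.

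**3. Bias of the unweighted mean.** Bias = (1 − response rate) × (respondent mean − non-respondent mean) = 0.66 × gap. The documents give no gap, so these are assumed values, set against the half-width of 1.52:

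| Assumed gap (points) | Bias (points) | Coverage of the 95% interval |
|---|---|---|
| 1 | 0.66 | about 86% |
| 2.3 | 1.52 | about 50% |
| 5 | 3.30 | about 1% |

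The break-even gap is 1.52 / 0.66 = 2.3 points. It applies only where all 2,750 respondents count. In Attachment B those are MH3a, SCP2 and SCP6, the indicators without an eligibility screen.

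**4. Screened indicators.** The CC indicators require more than one doctor's office or kind of service, IE2 and IE3 a visit summary, and IE4 to IE6 an overnight stay. As an example, assume 25% of children had a stay, with the same 34% response: n is about 688 of 2,020. The half-width is 1.96 × √(0.25 / 688) × √((2,020 − 688) / 2,019) = about 3.0 points, and the break-even gap is 3.0 / 0.66 = about 4.6 points.

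**5. What weighting on use could recover, and its cost (all assumed).** Let high-use children be 25% or 50% of those invited, responding at 40% to 50%, with the rest at 18% to 32% so that the total stays at 34%. Let the indicator differ by 10 to 20 points between the groups around a true 50%.
- Smallest case (25%, response 40% versus 32%, 10 points): unweighted estimate 50.4, bias 0.4.
- Half high-use, response 40% versus 28%, 10 to 20 points: bias 0.9 to 1.8.
- Largest case (50%, response 50% versus 18%, 20 points): unweighted estimate 54.7, bias 4.7.

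In this illustration response depends only on the use group, so weighting on it removes the whole bias. The design effect is 0.34 × (share / high-use response + (1 − share) / low-use response), which gives 1.01 to 1.28. The half-width becomes 1.52 × √1.01 = 1.52 up to 1.52 × √1.28 = 1.72.

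**The case against.** The strongest reply is that the plan already takes non-response seriously. It traces contact details through several sources, makes up to 10 call attempts, tabulates losses by reason, promises a participant flow diagram, and tests chart consent against perceived coordination. It also commits to a sensitivity analysis. All of this stands, but none of it brings prior use or disease burden into the check, and the consent test covers survey respondents only.

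Several stronger readings are tempting, and the documents do not support them:

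- A reader might infer that only unweighted results will be reported. The plan is silent on weights; the unspecified sensitivity analysis could be a reweighting, though only on the four listed variables.
- A reader might infer that the check is purely demographic. Diagnosis category is clinical, although it measures neither use nor severity.
- A reader might infer that bias will exceed sampling error across the survey. Every gap above is assumed. Many indicators are already limited to children with some recent service contact. That partly conditions on use, though not on its intensity, and raises the break-even gap.
- A reader might infer that weighting removes all the bias in step 3. That formula gives total non-response bias; weights remove only what the covariates explain.
- A reader might infer that weighted results must become the headline. The plan wants consistency with other users of the survey and, where appropriate, comparison with pilot data, so keeping unweighted results is a reasonable choice.
- A reader might infer that the data are in hand for every invited child and free to use. Linkage to the fee-for-service period is expected for over 95%. Consent to link survey answers is sought only at the end of the interview, and for opt-outs only a demographic summary is promised.

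**Conclusion.** The concern holds as a gap in the planned sensitivity analysis: its method is not stated, and its four variables omit prior use and disease burden, which the study will derive from claims for essentially the same children. That these variables relate to both response and reported coordination is plausible, not shown.

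The size of any bias cannot be found from the documents. An assumed 2.3-point gap would match the stated ±1.5 for MH3a, SCP2 and SCP6; screened indicators need a larger gap. Under the assumptions of step 5, selection on use alone would shift an all-caregiver indicator by 0.4 to 4.7 points. The ±1.5 should not be read as the full uncertainty, since it assumes random response. This is a worthwhile, low-cost improvement and not evidence that the survey results will be wrong.

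**What to change.** In the Aim 2 part of the section on statistical methods and sensitivity analysis for missing data:

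1. Specify a response-propensity model on the invited children, using age, gender, urban/rural residence, diagnosis category, CDPS group, and prior-year emergency department, inpatient, primary care and specialty use.
2. Report inverse-probability-weighted indicators beside the unweighted ones, which stay comparable with other implementations of the survey.
3. Do the same for chart consent among respondents, adding survey answers to the model. The planned test of consent against perceived coordination is a starting point.
4. State that the ±1.5 uses a finite population correction and assumes random response, and that weighting corrects only for the variables in the model.
5. Reword the sentence on differential missingness so that it does not read as a reason to omit the check.

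Cost: analysis time and slightly wider intervals, with the half-width going from 1.52 to between 1.52 and 1.72 under the assumed design effects. The plan must also confirm that response status, including that of families who opted out, may be joined to claims for this purpose. If opt-outs may not be joined, the model should cover the remaining families and the report should say so.
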